To compare baseline versus final evaluations, Wilcoxon test or paired t-test will be used in the case of dimensional variables, and McNemar test in the case of categorical variables. Intergroups comparisons will be performed using Mann Whitney test or Student t test for continuous variables and χ^2 test or Fisher's exact test for categorical variables. To determine the significance and strength of associations, Pearson's correlation coefficient will be used for analyses of associations between continuous variables and Spearman rank for nonparametric variables. Linear regression analysis will be used to identify determinants of AGE accumulation. Cox proportional hazards models will be used to investigate the prognostic value of the accumulation of AGE for predicting mortality. A p-value less than or equal to 0.05 will be considered to have statistical significance.

Sample size calculation of Study 1 was performed by using the software nQuery Advisor v.6.0.

Sample size Study 1:

The primary outcome for sample size determination is one-year survival in relation to increased SAF levels in people on HD and PD. With a power of 80%, a two-sided alpha of 5% and an expected hazard ratio of 3.5 and 2.0 in people on PD and HD, respectively (based on similar findings of the studies of Kimura et al. [2014] and Siriopol et al. [2015]), 100 HD and 40 PD participants will be needed.

Sample size Study 2

Since this is a proof of principle study, it would be reasonable to include 40 dialysis participants (either HD or PD).

Assessment of efficacy

Primary endpoints

Study 1:

- Mean change in SAF levels (AU) from baseline to 12 months of follow-up.
- One-year survival.

Study 2:

Mean change in SAF levels (AU) after 6 months of a dietitian supervised intensive nutritional support intervention

Secondary endpoints

Study 1:

- Regression coefficients for identifying factors associated with the accumulation of AGE.
- Correlation coefficients for analysing the association of SAF levels with morbidity, biochemistry, circulating AGE levels, inflammatory biomarkers, visual function, health-related quality of life and nutritional status.

Study 2:

- Changes in biochemistry, circulating AGE levels, inflammatory biomarkers, visual function, health-related quality of life and nutritional status.

Assessment of safety

Tolerability and safety of the nutritional support intervention during the proof of principle study (Study 2) will be assessed by direct interview. If any serious adverse event (SAE) is reported during the study, it will be recorded on an appropriate SAE report form.

Procedures for missing, unused and spurious data

All SAF measurements, biochemistry, nutritional and quality of life assessments for Study 1 and 2 will be used in the statistical analysis, including data from participants who did not complete the entire study protocol.

Definition of populations analysed

Study 1:

Full Analysis set: All participants included in the protocol for whom at least one post-baseline assessment of the primary endpoint is available.

Per protocol set: All participants in the Full Analysis set who are deemed to have no major protocol violations that could interfere with the objectives of the study.

Study 2:

Full Analysis set: All randomised participants, who participated in at least one treatment and for whom at least one post-baseline assessment of the primary endpoint is available.

Per protocol set: All participants in the Full Analysis set who are deemed to have no major protocol violations that could interfere with the objectives of the study.

ADVERSE EVENTS

The occurrence of an adverse event as a result of participation within this study is not expected and as such no adverse event data will be collected.

ETHICAL AND REGULATORY ASPECTS

ETHICS COMMITTEE AND REGULATORY APPROVALS

The study will not be initiated before the protocol, informed consent forms and participant information sheets have received approval / favourable opinion from the REC, and the respective NHS Research & Development (R&D) department. Should a protocol amendment be made that requires REC approval, the changes in the protocol will not be instituted until the amendment and revised informed consent forms and participant information sheets (if appropriate) have been reviewed and received approval / favourable opinion from the REC and R&D departments. A protocol amendment intended to eliminate an apparent immediate hazard to participants may be implemented immediately providing that the REC are notified as soon as possible and an approval is requested. Minor protocol amendments only for logistical or administrative changes may be implemented immediately; and the REC will be informed.

The study will be conducted in accordance with the ethical principles that have their origin in the Declaration of Helsinki, 1996; the principles of GCP, and the Department of Health Research Governance Framework for Health and Social care, 2005.

INFORMED CONSENT AND PARTICIPANT INFORMATION

The process for obtaining participant informed consent will be in accordance with the REC guidance, GCP and any other regulatory requirements that might be introduced. The investigator or their nominee and the participant shall both sign and date the Informed Consent Form before the person can participate in the study.

The participant will receive a copy of the signed and dated forms and the original will be retained in the Trial Master File. A second copy will be filed in the participant's medical notes and a signed and dated note made in the notes that informed consent was obtained for the study.

The decision regarding participation in the study is entirely voluntary. The investigator or their nominee shall emphasize to them that consent regarding study participation may be withdrawn at any time without penalty or affecting the quality or quantity of their future medical care, or loss of benefits to which the participant is otherwise entitled. No study-specific interventions will be done before informed consent has been obtained.

The investigator will inform the participant of any relevant information that becomes available during the course of the study, and will discuss with them, whether they wish to continue with the study. If applicable they will be asked to sign revised consent forms.

If the Informed Consent Form is amended during the study, the investigator shall follow all applicable regulatory requirements pertaining to approval of the amended Informed Consent Form by the REC and use of the amended form (including for ongoing participants).

RECORDS

Case Report Forms

Case Report Forms (CRFs) will be the primary data collection instrument. All data requested on the CRF will be recorded. Data collected includes inclusion and exclusion criteria, demographic characteristics, educational level, occupation status, family history, duration of renal replacement therapy, dialysis adequacy, aetiology of CKD, medical history (e.g. history of cardiovascular disease, diabetes and hypertension), current co-morbidities, alcohol history, smoking status, current medication, type of PD, volume of PD solutions SAF measurements, routine blood tests, circulating AGE levels, inflammatory biomarkers, visual function, nutritional and quality of life assessments.

Each participant will be assigned a study identity code number for use on CRFs, other study documents and the electronic database. The documents and database will also use their initials (of first and last names separated by a hyphen or a middle name initial when available) and final two digits from their year of birth.

CRFs will be treated as confidential documents and held securely in accordance with regulations. The investigator will make a separate confidential record of the participant's name, date of birth, local hospital number or NHS number, and Participant Study Number (the Trial Recruitment Log), to permit identification of all participants enrolled in the study, in accordance with regulatory requirements and for follow-up as required.

CRFs shall be restricted to those personnel approved by the Chief or local Principal Investigator and recorded on the 'Trial Delegation Log.'

All paper forms shall be filled in using black ballpoint pen. Errors shall be lined out but not obliterated by using correction fluid and the correction inserted, initialled and dated.

The Chief or local Principal Investigator shall sign a declaration ensuring accuracy of data recorded in the CRF.

Sample Labelling

Each participant will be assigned a study identity code number for use on the samples, consent forms and other study documents and the electronic database. The identifier will include subject number, participant initials (of first and last names separated by a hyphen or a middle name initial when available) and final two digits from their year of birth.

Source documents

Source documents shall be filed at the investigator's site and may include but are not limited to, consent forms, current medical records, laboratory results and records. A CRF may also completely serve as its own source data. Only study staff as listed on the Delegation Log

shall have access to study documentation other than the regulatory requirements listed below.

Direct access to source data / documents

The CRF and all source documents, including progress notes and copies of laboratory and medical test results shall be made available at all times for review by the CI, Sponsor's designee and inspection by relevant regulatory authorities (e.g. DH, Human Tissue Authority).

DATA PROTECTION

All study staff and investigators will endeavour to protect the rights of the study's participants to privacy and informed consent, and will adhere to the Data Protection Act, 1998. The CRF will only collect the minimum required information for the purposes of the study. CRFs will be held securely, in a locked room, or locked cupboard or cabinet. Access to the information will be limited to the study staff and investigators and relevant regulatory authorities (see above). Computer held data including the study database will be held securely and password protected. All data will be stored on a secure dedicated web server. Access will be restricted by user identifiers and passwords (encrypted using a one way encryption method).

Information about the study in the participant's medical records/hospital notes will be treated confidentially in the same way as all other confidential medical information.

Electronic data will be backed up every 24 hours to both local and remote media in encrypted format.

QUALITY ASSURANCE & AUDIT

INSURANCE AND INDEMNITY

Insurance and indemnity for study participants and study staff is covered within the NHS Indemnity Arrangements for clinical negligence claims in the NHS, issued under cover of HSG (96)48. There are no special compensation arrangements, but study participants may have recourse through the NHS complaints procedures.

The University of Nottingham as research Sponsor indemnifies its staff, research participants and research protocols with both public liability insurance and clinical trials insurance. These policies include provision for indemnity in the event of a successful litigious claim for proven non-negligent harm.

TRIAL CONDUCT

Study conduct may be subject to systems audit of the Trial Master File for inclusion of essential documents; permissions to conduct the study; Trial Delegation Log; CVs of study staff and training received; local document control procedures; consent procedures and recruitment logs; adherence to procedures defined in the protocol (e.g. inclusion / exclusion criteria, correct randomisation, timeliness of visits); AE recording and reporting; accountability of study materials and equipment calibration logs.

The Study Coordinator/Academic Supervisor, or where required, a nominated designee of the Sponsor, shall carry out a site systems audit at least yearly and an audit report shall be made to the Trial Steering Committee.

TRIAL DATA

Monitoring of study data shall include confirmation of informed consent; source data verification; data storage and data transfer procedures; local quality control checks and procedures, back-up and disaster recovery of any local databases and validation of data manipulation. The Study Coordinator/Academic Supervisor, or where required, a nominated designee of the Sponsor, shall carry out monitoring of study data as an ongoing activity.

Entries on CRFs will be verified by inspection against the source data. A sample of CRFs (10% or as per the study risk assessment) will be checked on a regular basis for verification of all entries made. In addition, the subsequent capture of the data on the study database will be checked. Where corrections are required these will carry a full audit trail and justification.

Study data and evidence of monitoring and systems audits will be made available for inspection by REC as required.

RECORD RETENTION AND ARCHIVING

In compliance with the ICH/GCP guidelines, regulations and in accordance with the University of Nottingham Research Code of Conduct and Research Ethics, the Chief or local Principal Investigator will maintain all records and documents regarding the conduct of the study. These will be retained for at least 7 years or for longer if required. If the responsible investigator is no longer able to maintain the study records, a second person will be nominated to take over this responsibility.

The Trial Master File and study documents held by the CI on behalf of the Sponsor shall be finally archived at secure archive facilities at the University of Nottingham. This archive shall include all study databases and associated meta-data encryption codes.

DISCONTINUATION OF THE TRIAL BY THE SPONSOR

The Sponsor reserves the right to discontinue this study at any time for failure to meet expected enrolment goals, for safety or any other administrative reasons. The Sponsor shall take advice from the Trial Steering Committee and Data Monitoring Committee as appropriate in making this decision.

STATEMENT OF CONFIDENTIALITY

Individual participant medical information obtained as a result of this study is considered confidential and disclosure to third parties is prohibited with the exceptions noted above. Participant confidentiality will be further ensured by utilising identification code numbers to correspond to treatment data in the computer files. Such medical information may be given to the participant's medical team and all appropriate medical personnel responsible for the participant's welfare.

If information is disclosed during the study that could pose a risk of harm to the participant or others, the researcher will discuss this with the CI and where appropriate report accordingly.

Data generated as a result of this study will be available for inspection on request by the participating physicians, the University of Nottingham representatives, the REC, local R&D Departments and the regulatory authorities.

PUBLICATION AND DISSEMINATION POLICY

The results of this study will be submitted to peer-reviewed journals for publication as soon as data analysis is completed. The results will also be presented at national and international scientific conferences. Participants will not be identified in any publications. Participants will be contacted either by email or a letter sent to their addresses about the findings of the research (unless participants advise the research team that they do not wish to be contacted). In addition, participants will be informed of the results of the study via a departmental research newsletter, which is made available to all people on dialysis. The results of this study will form part of PhD thesis for [name]. The study has been registered on www.clinicaltrials.gov (Trial registration number: NCT02878317)

USER AND PUBLIC INVOLVEMENT

Currently a patient focus group including people on HD is being established.

STUDY FINANCES

Funding source

This study is funded by internal funds from the University of Nottingham and Department of Renal Medicine, Royal Derby Hospital.

Participant stipends and payments

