Nevertheless, analysis of baseline data from Study 1 has identified strong associations between higher SAF and malnutrition whereas no correlations were observed between higher SAF and high dietary AGE intake. Correction of malnutrition may therefore represent a more important dietary intervention to reduce accumulation of AGE in people receiving dialysis. We further reasoned that placing people with malnutrition on a restrictive diet may worsen their malnutrition and we have therefore adapted our original research plan to include an observational study to assess the impact of correcting malnutrition on SAF by providing a dietitian supervised nutritional support intervention, which essentially involves the usual/standard dietetic care/advice provided by the NHS with some additional supervision, follow-up and approved dietary supplements (also provided by the NHS), rather than a randomised trial of dietary AGE restriction.

The results from the present project will benefit people on dialysis because they may demonstrate that the correction of malnutrition decreases the SAF levels in this population. Published observational studies suggest that reduction of SAF levels will in turn be associated with a reduction in the high morbidity and mortality rates associated with chronic dialysis and, consequently, healthcare costs. Improved survival and reduced comorbidity would also be expected to improve the quality of life of people on dialysis.

TRIAL / STUDY OBJECTIVES AND PURPOSE

PURPOSE

The purpose of the present project is to investigate the association between AGE accumulation and adverse outcomes (mainly mortality) and the impact of a dietary intervention on SAF levels in people on HD and PD.

PRIMARY OBJECTIVES

Study 1:

- To investigate whether the SAF levels increase over time in prevalent and incident HD and PD participants.
- To investigate one-year survival in relation to increased SAF levels.

Study 2:

- To investigate whether the correction of malnutrition by an intensive nutritional intervention results in a decrease in SAF levels in people on PD and HD.

SECONDARY OBJECTIVES

Study 1:

- To determine the most important factors associated with change in SAF over time.
- To investigate the association of increased SAF levels with morbidity, health-related quality of life and nutritional status.
- To investigate the association between SAF levels and changes in visual function.

Study 2:

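### Study 1's one-year survival analysis leaves its SAF exposure and hazard-ratio unit undefined, and its analysis set, if read as requiring a later SAF reading, removes deaths before 3 months

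*Combined protocol and SAP*

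**What the plan says.** Under Primary Objectives, Study 1 has two aims: "To investigate whether the SAF levels increase over time in prevalent and incident HD and PD participants", and "To investigate one-year survival in relation to increased SAF levels". The endpoints to match are the mean SAF change from baseline to 12 months and one-year survival.

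Under Statistics, Methods, Cox models are to examine the "prognostic value of the accumulation of AGE for predicting mortality". The covariate is not described further: baseline value, change, time-updated value and category are all left open.

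The sample-size paragraph states: "The primary outcome for sample size determination is one-year survival in relation to increased SAF levels in people on HD and PD". It gives 80% power, a two-sided 5% alpha, an "expected hazard ratio of 3.5 and 2.0 in people on PD and HD, respectively", and from these 100 HD and 40 PD participants. It does not give one-year mortality, a number of deaths, the share of participants with increased SAF, or the contrast to which the hazard ratios refer.

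Under Definition of populations analysed, the Study 1 Full Analysis set consists of participants "for whom at least one post-baseline assessment of the primary endpoint is available". The per-protocol set is a subset of it, and no other population is defined. Year-one SAF readings are at baseline, 3, 6, 9 and 12 months, each visit with three measurements. The exclusion criteria bar people expected to survive less than one year.

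**The concern.** One-year survival is the endpoint on which Study 1 was sized, and three things that determine its analysis are not fixed.

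- **Who is analysed.** An entry rule based on a later reading suits the SAF-change endpoint. Applied to survival, it selects on the outcome: a participant must live long enough to be re-measured before counting.
- **What the exposure is.** A baseline SAF value is known for everyone at time zero. A baseline-to-12-month change is known only for people alive at 12 months, so it cannot serve as a predictor of deaths in those 12 months.
- **What the hazard ratios mean.** The deaths needed for 80% power differ fourfold between a 50:50 split and a per-SD effect, so the stated power cannot be judged until the unit is known.

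At stake are an overstated one-year survival, the loss of deaths from a study that will have few, and a power claim that may or may not hold.

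**Working it through.** **1. The plan's own figure.** The stated inputs are 80% power, two-sided 5%, and hazard ratios of 2.0 (HD) and 3.5 (PD). They fix a number of deaths once a contrast is chosen, but not a number of participants. The figures of 100 and 40 therefore cannot be reproduced. What can be computed is the mortality they imply.

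**2. Deaths needed.** (1.960 + 0.842)² = 7.849; ln(2.0)² = 0.4805; ln(3.5)² = 1.5694.

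*50:50 high/low split* (Schoenfeld): deaths = 7.849 / (0.25 × ln(HR)²).
- HD: 7.849 / (0.25 × 0.4805) = 65.3, or 65% of 100.
- PD: 7.849 / (0.25 × 1.5694) = 20.0, or 50% of 40.
- Freedman's formula gives 71 and 26. Unequal splits need more: at 1:3, 88 and 27 by Schoenfeld.

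*Continuous SAF, hazard ratio per SD*: deaths = 7.849 / ln(HR)².
- HD: 7.849 / 0.4805 = 16.3, or 16.3% of 100.
- PD: 7.849 / 1.5694 = 5.0, or 12.5% of 40.

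*Continuous SAF, hazard ratio per 1 AU*: divide the per-SD figures by SD². The documents give no SD. For an assumed SD of 0.5 to 1.0 AU, HD needs 65.3 down to 16.3 deaths and PD 20.0 down to 5.0.

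**3. Power at assumed mortality.** The documents give no mortality, so 10-20% is an assumption. Power = Φ(√(k × deaths) × ln(HR) − 1.960), with k = 0.25 for the split and 1 per SD.

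| Assumed one-year mortality | HD deaths | HD, split | HD, per SD | PD deaths | PD, split | PD, per SD |
|---|---|---|---|---|---|---|
| 10% | 10 | 19% | 59% | 4 | 24% | 71% |
| 15% | 15 | 27% | 77% | 6 | 34% | 87% |
| 20% | 20 | 34% | 87% | 8 | 43% | 94% |

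At 30% mortality the split gives 48% (HD) and 58% (PD). With so few PD deaths the large-sample formula is only a guide.

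**4. Deaths lost if the analysis set requires a later SAF reading.** With one-year mortality m and a constant hazard, the share of first-year deaths falling before 3 months is (1 − (1 − m)^0.25) / m.
- m = 10%: 0.0260 / 0.10 = 26%.
- m = 20%: 0.0543 / 0.20 = 27%.
- m = 30%: 0.0853 / 0.30 = 28%.

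**5. What that does, for 100 HD at an assumed 15%.** Deaths before 3 months: 100 × (1 − 0.85^0.25) = 3.98. That leaves 11.02 deaths among 96.02 participants, so one-year survival reads 1 − 11.02/96.02 = 88.5% instead of 85%. Per-SD power falls from 77% to Φ(√11.02 × 0.6931 − 1.960) = Φ(0.341) = 63%. The hazard ratio then describes people who have already survived 3 months. Under proportional hazards that mainly costs precision; if the SAF effect differs early on, it changes the answer.

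**The case against.** The strongest reply is that the exposure is clear enough in context. The background describes SAF as a measure of AGE accumulation in skin, and the Study 1 procedures use the same term for the SAF reading, so the Cox sentence most naturally concerns a level. The secondary objective on increased SAF levels and morbidity reappears in the endpoint lists simply as SAF levels, and change over time has its own wording. This stands. A reader might infer that the plan means to predict deaths from a rise in SAF, with immortal-time bias built in. The documents do not support that: no section plans such an analysis. Even a rise is unusable only in its baseline-to-12-month form, since rises to 3, 6 or 9 months could enter as time-updated values. What remains missing is an explicit statement of baseline timing and scale.

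The second reply is that one-year survival is itself a primary endpoint, so a recorded death could count as the required post-baseline assessment; the missing-data section also keeps data from non-completers. The rule is therefore ambiguous, and loss of early deaths is not certain. But if a death qualifies, the rule excludes hardly anyone; it has practical effect only when it refers to SAF. The missing-data section lists SAF, biochemistry, nutrition and quality of life, not survival, so it does not settle the matter.

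Third, the plan mentions no cut-off, and on a per-SD reading its numbers are of the right order. That also stands.

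**Conclusion.** The point holds as an under-specified primary analysis with one rule that needs changing. If the Full Analysis set refers to SAF, the survival analysis loses about 26-28% of first-year deaths. This rests on a constant hazard and an assumed 10-30% mortality; the share would be larger if deaths cluster early and smaller if the exclusion for short expected survival thins them out.

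A reader might go further and infer that 80% power is out of reach. The documents do not support this, because they give neither mortality nor the hazard-ratio contrast. A 50:50 split would need about 65% (HD) and 50% (PD) one-year mortality, which is hard to square with excluding people expected to live less than a year, but it is not arithmetically impossible. On a per-SD reading the stated numbers are plausible: about 16% and 12.5% mortality would suffice. The power claim is thus unverifiable as written and depends on a unit the plan omits.

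**What to change.** In the statistics section:

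1. Define the one-year survival population as all enrolled Study 1 participants, followed from baseline, with no post-baseline assessment required. Keep the present Full Analysis set for the SAF-change endpoint.
2. Name the Cox exposure: baseline SAF, the mean of the three readings, continuous, with the hazard ratio per SD or per 1 AU.
3. Use rises in SAF only as a time-updated covariate from the 3-, 6-, 9- and 12-month readings, or in a 12-month landmark analysis of deaths during the later follow-up to five years.
4. Restate the sample-size basis for HD and PD separately: hazard-ratio unit, assumed one-year mortality, expected deaths, and power over a labelled range of mortality such as the table above.

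The cost is a few sentences and no extra SAF measurements. Date of death or last contact must be available for every enrolled participant; the list of data under Case Report Forms does not name it, so it should be added there. A continuous hazard ratio is slightly harder to present than a high/low comparison.
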